### **6.3. Other Endpoint(s)**

#### **6.3.1. SARS-CoV-2 Viral Load**

Absolute and changes from baseline in nasopharyngeal swab and saliva viral load will be summarized by treatment and time post-dose. Baseline is as defined in [Section 3.3.1](#).

Individual and mean plots will be produced for absolute and changes from baseline in nasopharyngeal swab and saliva viral load by treatment.

The percentage of participants who have viral load detectable at baseline and undetectable (<BLQ for both nasopharyngeal swab and saliva) at 24 hours after the end of the infusion (i.e. at the FU #1 visit) will be produced by treatment.

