### 3.3. Other Endpoint(s)

#### 3.3.1. SARS-CoV-2 Viral Load

Nasopharyngeal swab and saliva samples will be collected according to the SoA given in the protocol.

Baseline will be the last pre-dose measurement.

The following viral load endpoints will be determined and reported as separate endpoints:

- Change from baseline in nasopharyngeal swab and saliva viral load

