#### **5.2.1. Analyses for Continuous Endpoints**

Continuous variables will be presented using summary statistics: number of observations, arithmetic mean, standard deviation, median, minimum and maximum values.

Log transformed continuous variables will be presented using summary statistics: number of observations, arithmetic mean, median, cv%, standard deviation, minimum, maximum, geometric mean and geometric cv%.

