#### **5.2.2. Analyses for Categorical Endpoints**

Categorical variables will be presented using summary statistics: number of observations and percentages.

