**Table 5. PK Parameters to be Summarized Descriptively for Part 2: MAD**

| Parameter   | Summary Statistics   |
|---|--|
| $C_{120}$ , $C_{max}$ , $T_{max}$ , $C_{ss}$ , $C_{120}$ (dn) and $C_{ss}$ (dn) | N, arithmetic mean, median, cv%, standard deviation, minimum, maximum, geometric mean and geometric cv%. |
| $t_{1/2}$   | N, arithmetic mean, median, cv%, standard deviation, minimum, maximum.                                   |

There will be one summary table for each analyte presenting all PK parameters. This will include data from all cohorts and will be presented by dose.

To assess the relationship between the PK parameters and dose, dose normalized  $C_{120}$  and  $C_{ss}$  (**Part 2: MAD**) of PF-07304814 and PF-00835231 will be plotted against dose (using a logarithmic scale), and will include individual participant values and the geometric means for each dose. Geometric means will have a different symbol than the individual values. The values will be dose normalized (to a 1 mg dose) by dividing the individual values and raw geometric means by dose. A footnote will be added to the plots to indicate that geometric means are presented and that data from all cohorts are presented on the plot. Dose normalized  $C_{120}$  and  $C_{ss}$  (**Part 2: MAD**) for both analytes will be listed along with other individual PK parameters.

Supporting data from the estimation of  $t_{1/2}$  will be listed by analyte and dose where applicable: terminal phase rate constant ( $k_{el}$ ); goodness of fit statistic from the log-linear regression ( $r^2$ ); the percent of  $AUC_{inf}$  based on extrapolation ( $AUC_{extrap\%}$ ); and the first, last, and number of time points used in the estimation of  $k_{el}$ . These data may be included in the CSR.

Presentations for PF-07304814 and PF-00835231 concentrations will be presented by analyte using participants in the PK concentration analysis set (as defined in Section 4) will include:

- a listing of all concentrations sorted by participant ID, dose and nominal time post-dose. The concentration listing will also include the actual times. Deviations from the nominal time will be given in a separate listing.
- a summary of concentrations by dose and nominal time post-dose, where the set of statistics will include n, mean, median, standard deviation, coefficient of variation (cv), minimum, maximum and the number of concentrations above the lower limit of quantification.

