- individual concentration-time plots by dose (on both linear and semi-log scales) against actual time post-dose (there will be separate spaghetti plots for each dose per scale).
- median concentrations-time plots (on both linear and semi-log scales) against nominal time post-dose by dose (all doses on the same plot per scale, based on the summary of concentrations by dose and time post-dose).
- mean concentrations-time plots (on both linear and semi-log scales) against nominal time post-dose by dose (all doses on the same plot per scale, based on the summary of concentrations by dose and time post-dose).

The scale used for the x-axis (time) of these plots will be decided on review of the data, and will depend on how long PF-07304814 and PF-00835231 concentration is quantifiable in the matrix.

For summary statistics, median and mean plots by sampling time, the nominal PK sampling time will be used, for individual participant plots by time, the actual PK sampling time will be used.

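### Does the viral load section of the SAP need a stated log scale and a fixed denominator for the clearance percentage?

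*SAP*

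**What the plan says.** Protocol 9.4.3 leaves the analysis of exploratory endpoints to the SAP. Protocol 8.8.3 says that swab and saliva viral load is measured by RT-PCR; it gives no unit.

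- **Endpoint.** SAP 3.3.1 defines change from baseline in swab and saliva viral load, introduced by "The following viral load endpoints will be determined and reported as separate endpoints".
- **Summaries.** SAP 6.3.1: "Absolute and changes from baseline in nasopharyngeal swab and saliva viral load will be summarized by treatment and time post-dose". Individual and mean plots follow, with no axis scale.
- **Default statistics.** SAP 5.2.1: "Continuous variables will be presented using summary statistics: number of observations, arithmetic mean, standard deviation, median, minimum and maximum values". A second set, with geometric mean, opens "Log transformed continuous variables will be presented using summary statistics". Viral load is not assigned to it. SAP Tables 2 and 3 assign an analysis scale to PK parameters only.
- **Clearance.** SAP 6.3.1 also plans "The percentage of participants who have viral load detectable at baseline and undetectable" at the first follow-up visit, where undetectable means below quantification in both swab and saliva. For categorical variables SAP 5.2.2 says "Categorical variables will be presented using summary statistics: number of observations and percentages".
- **Values below quantification.** Under SAP 5.3 they are set to the LLQ in viral load summaries and plots, and marked as below the LLQ in listings. PK concentration summaries in SAP 6.2 also report "the number of concentrations above the lower limit of quantification"; no such count is named for viral load.

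**The concern.** Viral load can span several orders of magnitude. On a linear scale, one participant with a high baseline can supply most of a group mean in a cohort of 6 active and 2 placebo. The SAP shows that its authors had the log scale in mind for PK, where it plans "mean concentrations-time plots (on both linear and semi-log scales) against nominal time post-dose by dose". Its silence for viral load can therefore look like a choice of the untransformed default.

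The clearance percentage can be computed in several ways from the same data. Its base could be all participants, those detectable at baseline, or those who also have a follow-up sample, and the baseline specimen is not named. Over all participants, the percentage cannot exceed the share detectable at baseline, so two arms that differ in that share would not be comparable.

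An undetectable baseline sample is possible. Protocol 5.1 accepts an antigen test in any specimen, blood included, and protocol 4.1 allows symptom onset up to 15 days before Screening. Protocol 4.2 names viral load among the measures for exploring antiviral activity, so a misleading display would matter to whoever reads that signal.

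**Working it through.** The documents give no viral load figure to reproduce. Every viral load input below is an assumption; only the group sizes come from the protocol (9.2: 6 active and 2 placebo per cohort).

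**1. How far one participant can dominate a linear mean.** Assume log10 viral load is normal with SD s, so x = 10^(log10 value). The share of the largest value is max(x) / sum(x). Medians over 200,000 simulated samples:

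| Assumed s (log10) | 0.5 | 1.0 | 1.5 | 2.0 |
|---|---|---|---|---|
| n = 6 | 43% | 64% | 79% | 88% |
| n = 2 | 75% | 90% | 96% | 99% |

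The weakness of a linear mean is real. It applies only if the unit is linear.

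**2. What the planned tables would still show on a linear scale.** Take six assumed baselines of 8, 7, 6, 5, 5, 4 log10 and drops of 0.3, 2, 2, 2, 2, 1.

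- Mean log10 change: -(0.3 + 2 + 2 + 2 + 2 + 1)/6 = -9.3/6 = -1.55.
- Baseline sum: 10^8 + 10^7 + 10^6 + 2 × 10^5 + 10^4 = 111,210,000. The first participant supplies 10^8 / 111,210,000 = 90%.
- Follow-up sum: 10^7.7 + 10^5 + 10^4 + 3 × 10^3 = about 50,231,700. The ratio of means is 50,231,700 / 111,210,000 = 0.452, or -0.35 log10. The mean understates the decline.
- Baseline median: (10^6 + 10^5)/2 = 550,000. Follow-up median: (10^4 + 10^3)/2 = 5,500. The ratio is 0.01, or -2 log10.

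The default set prints the median of absolute values at each visit, so in this example the decline is visible without a log scale.

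**3. Comparison between arms.** Assume baseline mean 5.5 log10 with SD 0.5 to 2.5, natural decline 1 log10 with SD 0.7 to 1.0, LLQ 2 log10, and a true extra decline of 1 log10 on active. Over 60,000 simulated cohorts per setting, the probability that the active group shows the larger fall is:

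| Active : placebo | Mean linear change | Median linear change | Mean log10 change |
|---|---|---|---|
| 6 : 2 | 69–74% | 43–58% | 84–96% |
| 6 : 8 (Part 2 placebo pooled over four cohorts) | 51–73% | 60–70% | 92–99.6% |

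Log10 is best, but the model adds the effect on the log10 scale, so that is largely built in. With no drug effect, the 6:2 mean linear change already gives 49–67% because the groups are unequal and the data skewed, so 69–74% is not a sensitivity. The planned absolute values also allow follow-up mean over baseline mean; at 6:8 that ratio gives the right direction in 81–97%. The linear tables hold more signal than the change columns suggest.

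**4. Clearance.** If u of 6 active participants are undetectable at baseline, the percentage over all 6 cannot exceed (6 - u)/6: 5/6 = 83%, 4/6 = 67% and 3/6 = 50% for u = 1, 2, 3. With u = 2 and two cleared, 2/4 = 50% against 2/6 = 33%. With u = 0 there is no distortion.

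The specimen rule can also move the figure. In one assumed set of six, joint clearance is 2/5 = 40% if either specimen must be detectable at baseline and 1/4 = 25% if both must be; over all six the same numerators give 33% and 17%. Read specimen by specimen, it is 3/5 = 60% for swab and 2/4 = 50% for saliva. The joint readings differ by one participant in the numerator and at most two in the base.

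The base can be recovered. SAP 5.2.2 puts a count beside the percentage: 2 with 33% implies 2/0.33 = 6, and 2 with 50% implies 2/0.50 = 4.

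**5. How open the wording is.** Requiring both specimens below quantification at follow-up most naturally means jointly; the separate-endpoints phrase in SAP 3.3.1 introduces the change from baseline, not this percentage. For Part 2, the note to inclusion criterion 3 asks for viral genetic material within 72 hours before Screening (with an exception where no repeat sample can be obtained), and a Part 2 schedule footnote asks for PCR testing in the same window. Undetectable baselines are therefore less likely in Part 2 than the general eligibility wording suggests, though still possible.

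**The case for a change.** The best case for a change is that the protocol hands this detail to the SAP and the SAP does not supply it. Two programmers could both follow section 6.3.1 and report different clearance percentages. The study is sponsor-open, so rules fixed in writing would remove discretion, and the cost is a few sentences with no new data. The median of the linear changes is no rescue, as step 3 shows.

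Most of this stands as description. The unit, the scale, the denominator and the baseline specimen are not stated, and log10 is the better scale if results are linear. The case does not show that a wrong scale was chosen: the laboratory unit is not in the documents, and all the performance figures rest on assumed inputs.

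The obvious repair to the denominator has a cost too. Requiring a follow-up sample excludes people on a post-randomisation event and could drop those who deteriorate or withdraw. Choosing between that base and all treated participants is a judgement. A printed count of values below quantification is a preference, since the listings already mark them.

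**Conclusion.** No change to the plan is called for. This is missing detail on an exploratory, descriptive endpoint. SAP 5.1 plans no test or decision rule, and escalation under protocol 6.6.1 rests on safety, tolerability and PK.

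A competent analyst would work in log10, or receive the data that way, and would show clearance as a count over a stated base. If the literal default were followed on a linear unit, the mean would be poor: at n = 6, one participant would supply a median 43% to 88% of the sum for assumed SDs of 0.5 to 2.0 log10. The same outputs would still carry medians, ranges, individual plots and listings from which a reader can rebuild the result. The clearance figure could shift, for example from 50% to 33% if 2 of 6 are undetectable at baseline, and the count beside it would expose the shift.

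Group sizes of 6 and 2 are nominal: enrolment to Cohort 1 was stopped when 4 participants had been dosed (protocol 4.3.2), and Cohort 2 was not conducted (SAP 3.2). With groups this small, no sound reader would draw a conclusion from either figure alone. This rests on the assumed inputs above and on ordinary practice in labelling tables.

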4. STUDY DESIGN

4.1. Overall Design

This is a First-In-Human Phase 1b study to evaluate the safety, tolerability and PK of PF-07304814 in participants who are hospitalized for treatment of COVID-19. The participants will be receiving SoC therapy for the treatment of mild, moderate, or severe COVID-19, but will not be eligible if they require mechanical ventilation or ECMO at screening or baseline. All participants will have a confirmed positive test for SARS-CoV-2 (see [Section 5.1](#) for additional details) and onset of symptoms within 15 days of Screening. For inclusion into **Part 2: MAD** of the study, participants will be required to have had a positive test for SARS-CoV-2 (See [Section 5.1](#) for details) within 72 hours prior to Screening.

This is a 2-part study in which up to a total of approximately 72 participants on SoC with the intervention such that approximately 72 evaluable participants complete the study. It is a randomized, double-blind, sponsor-open, parallel group, placebo-controlled trial.

Part 1: SAD is to evaluate safety, tolerability, and PK of escalating doses of PF-07304814 given as 24-hour IV infusions. Two planned and 3 optional cohorts with 8 participants/cohort will be included in **Part 1**. **Part 2: MAD** is to evaluate safety, tolerability, and PK of multiple ascending doses of PF-07304814 given as 120-hour IV infusions. Two planned and 2 optional cohorts with 8 participants/cohort will be included in **Part 2**.

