5.1. Inclusion Criteria

Participants are eligible to be included in the study only if all of the following criteria apply:

Age and Sex:

1. Male or female participants between the ages of 18 and 79 years, inclusive, at Screening.

Note: Participants aged 76 to 79 years of age should have BMI <35 kg/m².

- All fertile participants must agree to use a highly effective method of contraception.
- Refer to [Appendix 4: Contraceptive Guidance](#) for reproductive criteria for male ([Section 10.4.1](#)) and female ([Section 10.4.2](#)) participants.

Type of Participant and Disease Characteristics:

2. Participants who are willing and able to comply with all scheduled visits, treatment plan, laboratory tests, lifestyle considerations, and other study procedures.
3. Confirmed presence of SARS-CoV-2 infection as determined by RT- PCR or another method that measures SARS-CoV-2 viral genetic material or by specific SARS-CoV-2 antigen tests in any specimen (eg respiratory fluid sample, saliva, or blood).

Note: For **Part 2: MAD**, confirmed presence of SARS-CoV-2 viral genetic material in a sample must be ≤ 72 hours prior to Screening). A positive result from a test that was collected ≥ 72 hours prior to Screening may be accepted if the site is unable to obtain a repeat sample **CCI**

4. Hospitalized for treatment of COVID-19.

CC1

CC1

CC1

Weight:

6. Total body weight ≥ 50 kg (110 lb), BMI < 40 kg/m².

Note: Participants aged 76 to 79 years, inclusive, should have BMI < 35 kg/m².

Informed Consent:

7. Capable of giving signed informed consent as described in [Appendix 1](#), which includes compliance with the requirements and restrictions listed in the ICD and in this protocol.

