## 2.2. Study Design

This is a First-In-Human Phase 1b study to evaluate the safety, tolerability and PK of PF-07304814 in participants who are hospitalized for treatment of COVID-19. The participants will be receiving SoC therapy for the treatment of mild, moderate, or severe COVID-19, but will not be eligible if they require mechanical ventilation or ECMO at screening or baseline. All participants will have a confirmed positive test for SARS-CoV-2 and onset of symptoms within 15 days of Screening. For inclusion into **Part 2: MAD** of the study, participants will be required to have had a positive test for SARS-CoV-2 within 72 hours prior to Screening.

This is a 2-part study in up to a total of approximately 72 participants on Standard of Care (SoC) with the intervention such that approximately 72 evaluable participants complete the study. It is a randomized, double-blind, sponsor-open, parallel group, placebo-controlled trial. **Part 1: SAD** is to evaluate safety, tolerability, and PK of escalating doses of PF-07304814 given as 24-hour IV infusions. Two planned and 3 optional cohorts with 8 participants/cohort will be included in **Part 1**. **Part 2: MAD** is to evaluate safety, tolerability,

and PK with multiple ascending doses of PF-07304814 given as 120-hour IV infusions. Two planned and 2 optional cohorts with 8 participants/cohort will be included in **Part 2**.

**Figure 1.** Part 1: SAD (24-h Continuous IV Infusion)

Precautionary sentinel dosing will be used in each dose-escalating cohort in Part 1. A small cohort of 2 participants (1 receiving PF-07304814 and 1 receiving placebo) will be dosed prior to the remainder of the cohort.

Cohorts of 8 participants each who meet the eligibility criteria will be enrolled. The 2 sentinel participants will be randomized in a ratio of 1 (PF-07304814): 1 (placebo), while the remaining 6 participants will be randomized in a ratio of 5 (PF-07304814):1 (placebo).

[figure not shown]
All participants will follow the study procedures as outlined in Schedule of Activities (SoA). They will be required to stay in hospital from at a minimum, Day 1, pre-dose (at least 2 hours) through completion of Day 3 evaluations (Follow-up 1). Participants will then return for Day 6 (Follow-up 2) activities and a planned final follow-up visit per the SoA on Day 30-37 (Follow-up 3) for a total of approximately 4-5 weeks study participation from first dose to follow-up, excluding screening.

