## 4. ANALYSIS SETS (POPULATIONS FOR ANALYSIS)

Data for all participants will be assessed to determine if participants meet the criteria for inclusion in each analysis population prior to unblinding and releasing the database and classifications will be documented per standard operating procedures.

| Population  | Description   |
|---|---|
| Enrolled/Randomly assigned to study intervention | "Enrolled" means a participant's, or his/her legally authorized representative's, agreement to participate in a clinical study following completion of the informed consent process. Potential participants who are screened for the purpose of determining eligibility for the study, but do not participate in the study, are not considered enrolled, unless otherwise specified by the protocol. |
| Evaluable  | All participants randomly assigned to study intervention and who take at least 1 dose of study intervention for the given part of the study (Part 1: SAD or Part 2: MAD).   |
| Safety   | All participants randomly assigned to study intervention and who take at least 1 dose of study intervention for the given part of the study (Part 1: SAD or Part 2: MAD). Participants will be analyzed according to the product they actually received.  |
| PK Concentration Set                             | All participants randomly assigned to study intervention and who take at least 1 dose of study intervention and in whom at least 1 concentration value is reported for the given part of the study (Part 1: SAD or Part 2: MAD).  |
| PK Parameter Set                                 | All participants randomly assigned to study intervention and who take at least 1 dose of study intervention and in whom at least 1 of the PK parameters of interest are reported for the given part of the study (Part 1: SAD or Part 2: MAD).  |
| Biomarker Analysis Set                           | All participants randomly assigned to study intervention and who take at least 1 dose of study intervention and in whom at least 1 of the biomarkers of interest are reported for the given part of the study (Part 1: SAD or Part 2: MAD).   |

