### **5.3. Methods to Manage Missing Data**

For the analysis of safety endpoints, the sponsor data standard rules for imputation will be applied.

In all PK data presentations (except listings), concentrations below the limit of quantification (BLQ) will be set to zero.

In listings, BLQ values will be reported as “<LLQ”, where LLQ will be replaced with the value for the lower limit of quantification (LLQ).

For PK summary tables and plots of mean/median profiles, statistics will be calculated having set concentrations to missing if 1 of the following cases is true:

1. A concentration has been collected as ND (ie not done) or NS (ie no sample),
2. A deviation in sampling time is of sufficient concern or a concentration has been flagged anomalous by the pharmacokineticist/statistician.

For listing of viral load and cytokine data, BLQ values will be reported as “<LLQ”, where LLQ will be replaced with the value for the lower limit of quantification (LLQ). For summaries and plots BLQ values will be replaced with the value for the lower limit of quantification (LLQ).

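### Viral-load change from baseline is summarised with no quantifiable-baseline condition, so participants already at the assay floor at dosing can dilute or distort the comparison between arms

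*SAP*

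**What the plan says.** **Analysis.** SAP 6.3.1: "Absolute and changes from baseline in nasopharyngeal swab and saliva viral load will be summarized by treatment and time post-dose". Individual and mean plots of the same quantities follow. SAP 3.3.1 takes the last pre-dose value as baseline and reports swab and saliva as separate endpoints. SAP 5.3 adds, for viral load and cytokines: "For summaries and plots BLQ values will be replaced with the value for the lower limit of quantification (LLQ"). The Biomarker Analysis Set in SAP 4 needs only that "at least 1 of the biomarkers of interest are reported for the given part of the study", and SAP 6.4 rules out subset analyses. Within 6.3.1, only the percentage going from detectable to undetectable refers to baseline status.

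**Entry.** Protocol 5.1, criterion 3, accepts a positive test for viral genetic material or a positive result "by specific SARS-CoV-2 antigen tests in any specimen (eg respiratory fluid sample, saliva, or blood"). SAP 2.2 adds: "All participants will have a confirmed positive test for SARS-CoV-2 and onset of symptoms within 15 days of Screening". Screening may fall on Day -3. For Part 2, protocol 4.1 says "participants will be required to have had a positive test for SARS-CoV-2" in the 72 hours before Screening and points to 5.1 for details. The note in 5.1 then allows an exception: "A positive result from a test that was collected ≥ 72 hours prior to Screening may be accepted" where a repeat sample cannot be obtained; the remainder is redacted. Footnote a of the Part 2 Schedule of Activities (SoA) and SAP 2.2 state the 72-hour requirement without mentioning the exception.

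**The concern.** A positive entry test does not show that virus is quantifiable at dosing in the two specimens analysed. The qualifying specimen may be a different one, the test may be antigen-based, and symptoms may be up to 15 days old at Screening. Even under the main Part 2 rule, the positive specimen can be 3 days (72 hours) + 3 days (Screening to dosing) = 6 days old when infusion starts. The SAP foresees undetectable baselines, because its clearance percentage refers to participants detectable at baseline, but it does not carry that condition into the change tables and mean plots.

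With BLQ set to LLQ, a participant at the floor at baseline adds a zero or a rise to the arm mean whatever the drug does. Protocol 4.2 names viral load among the measures by which antiviral activity will be explored, and with 6 active and 2 placebo per cohort a single participant carries a lot of weight.

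**Working it through.** **Inputs**

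- BLQ rule: SAP 5.3. Baseline rule: SAP 3.3.1.
- Allocation: 6 active to 2 placebo per cohort. Part 1 reaches this as 1:1 sentinels plus 5:1 (protocol 4.1.1); Part 2 randomises 6:2 (4.1.2).
- Cohorts: 2 planned + 3 optional in Part 1, 2 planned + 2 optional in Part 2 (protocol 4.1). Check: (2 + 3) × 8 + (2 + 2) × 8 = 40 + 32 = 72, the stated maximum.
- Placebo: SAP 6 reports it by cohort in Part 1. SAP 6.1.3 and 6.1.4 plot a pooled placebo in Part 2. SAP 6.3.1 does not mention pooling.
- Not in the documents: the LLQ, the analysis scale, and the share p that is BLQ at baseline. I assume p between 0 and 0.5, and log10 units in the examples.

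**Step 1: the floor.** Recorded change = max(post, LLQ) − max(baseline, LLQ). If baseline is below LLQ, this is max(post, LLQ) − LLQ ≥ 0. It holds on the raw or the log scale.

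**Step 2: one arm.** If k of n participants are BLQ at baseline and stay BLQ, and the others have mean change m, the arm mean is (1 − k/n) × m.

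| Arm | k/n | Loss in mean change |
|---|---|---|
| Active, one cohort | 1/6 | 17% |
| Active, one cohort | 2/6 | 33% |
| Part 1 placebo, one cohort | 1/2 | 50% |
| Part 2 placebo, 2 cohorts pooled | 1/4 | 25% |
| Part 2 placebo, 4 cohorts pooled | 1/8 | 12.5% |

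**Step 3: the contrast.** With the same p in both arms, the expected difference is (1 − p) × the difference among participants with a quantifiable baseline. An assumed true difference of 1.0 log10 becomes 0.90, 0.80, 0.70, 0.60 and 0.50 at p = 0.1, 0.2, 0.3, 0.4 and 0.5.

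In a single 6:2 cohort the shares need not match. Assume declines of 2 (active) and 1 (placebo) log10, a true difference of 1.0:

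- 2/6 active and 0/2 placebo BLQ: (4/6) × 2 − 1 = 0.33
- 3/6 active and 0/2 placebo BLQ: (3/6) × 2 − 1 = 0
- 0/6 active and 1/2 placebo BLQ: 2 − (1/2) × 1 = 1.5

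**Step 4: how often.** At an assumed p = 0.3, at least one of 6 active is BLQ at baseline with probability 1 − 0.7^6 = 0.88, and at least one of 2 placebo with probability 1 − 0.7^2 = 0.51. At p = 0.1 these are 0.47 and 0.19.

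**Step 5: what restriction recovers.** Restricting to quantifiable baselines removes the (1 − p) factor. Precision gains little. With 24 active and 8 placebo, SD 1.5 and declines of 2 and 1 log10 (all but the counts assumed), difference/SE is 1.36 for all participants and 1.46 for the restricted group at p = 0.2, and 0.98 and 1.15 at p = 0.5.

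Restriction also leaves the floor in place for participants who start just above LLQ. In a simulation with an assumed effect of 1 log10, 25% BLQ at baseline gave 0.39 in all participants and 0.51 in the quantifiable group; 9% BLQ gave 0.62 and 0.68.

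**The case against.** The strongest reply is that little hangs on this and that the plan already exposes it. Viral load is a tertiary endpoint. There are no hypotheses or statistical decision rules, and escalation rests on safety, tolerability and PK. SAP 6.3.1 provides individual plots of absolute values and changes, listings show BLQ results as such, and summaries include median, minimum and maximum. With about 6 active participants per cohort, a careful reader can see who began at the floor. All of this stands and limits the importance of the point. It does not correct the arm means and mean plots, and no count of BLQ baselines by arm is specified.

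Two replies on entry also stand in part. Criterion 5 and the end of the criterion 3 note are redacted, so a reader might infer that older tests are accepted without any age limit, but the visible text cannot show that. A reader might also see protocol 4.1 as contradicting 5.1; because 4.1 refers to 5.1 for details, 5.1 can be read as qualifying it. The wording that remains to be reconciled is in SoA footnote a and SAP 2.2, which state the 72-hour condition without that reference.

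Finally, restriction could leave 0 or 1 placebo participants in a Part 1 cohort. That is a reason to add the restricted summary beside the full one, not to replace it.

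**Conclusion.** The point holds as an inexpensive improvement to a descriptive, exploratory analysis. The floor result in Step 1 is exact. That the summaries cover everyone is inferred: 6.3.1 names no analysis set, and no visible text restricts on baseline. The size depends on p, on affected participants remaining BLQ, and on the documents' unstated LLQ. The expected effect is dilution to about (1 − p), with chance distortion in either direction within a single cohort.

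A reader might infer that the rule masks any antiviral effect. The documents do not support that: dilution is partial, and one BLQ placebo participant can inflate the contrast, as the 1.5 in Step 3 shows. Nor does the 50% loss apply to placebo throughout. It fits one Part 1 cohort; if Part 2 placebo is pooled for viral load as it is in the vital-sign and ECG plots, the loss per participant is 25% to 12.5%.

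**What to change.** In SAP 6.3.1, for each specimen:

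- add change-from-baseline tables and mean plots restricted to participants with a quantifiable baseline in that specimen;
- report n and the number BLQ at baseline by treatment;
- keep the all-participant summary alongside.

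Name this analysis in SAP 6.4 as an exception, so that it is prespecified and consistent with the bar on subset analyses.

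Separately, reconcile the 72-hour wording in SoA footnote a and SAP 2.2 with the exception in protocol 5.1.

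The cost is SAP wording, one flag derived from samples already scheduled before dosing, and a few extra outputs. The flag uses only a pre-dose value, so it adds no selection on post-treatment outcome. The downside is smaller n.
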